## **OBJECTIVES**

### **PRIMARY**

Investigate the effect of daily ingestion of fermented milk containing 40 billion LcS on the changes in the concentration of salivary IgA in amateur triathletes participating in this study, before and after an official triathlon competition.

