## **TRIAL DESIGN**

The study is designed as a multi-center, randomized, controlled, researcher and volunteer blinded, with two parallel groups (intervention and placebo). In addition, the randomization will be performed as block randomization with a 1:1 allocation.

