## Population and design of the study

In order to perform this research project, it is proposed to recruit and select 70-80 amateur triathletes, between 25 to 45 years, both sexes, residing in the city of São Paulo, Brazil, who will be participating in the same triathlon competition.

Regarding the sample size, it was determined using G\*Power software (version 3.1.9.6). The analysis was conducted using the F tests - ANOVA: repeated measures, within-between interaction option to accommodate the mixed design of the study, which includes two groups and five repeated measurements. It is important to mention that to carry out the sample size calculation alignment with the study's primary objective, which is associated with the salivary IgA, we used the data presented in the study performed by [name] et al., 2019. In agreement with this data, the following parameters were used to calculate the required sample size: Effect size (f): 0.15 ([name] et al., 2019). Alpha error probability ( $\alpha$ ): 0.05. Power (1- $\beta$  error probability): 0.85. Correlation among repeated measures: 0.5. Nonsphericity correction ( $\varepsilon$ ): 1. Based on these inputs, the total sample size required to achieve the desired power of 0.85 is 62 participants. Thus, 70-80 athletes will be included in this study. This sample size will be distributed equally between the two groups (35-40 participants per group).

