## **Cardiopulmonary Test**

The physical capacity of each volunteer will be characterized through a cardiopulmonary test that will be performed on a treadmill attached to the gas analyzer, with electrocardiography and gas analysis software. This test will be performed at the Research and Training Olympic Center, an institution belonging to the Municipal Secretariat of Sports, Leisure, and Recreation of the City of São Paulo.

In order to carry out the cardiopulmonary test, the patient's preparation rules will be followed, which include hair removal from the place where the electrodes will be placed, cleaning the skin with alcohol, and scarification with water sandpaper number 400. The placement of the electrodes will follow the described by Salient (2019) for the formation of the 12 leads in the Einthoven triangle.

The cardiopulmonary test will be performed with a ramp protocol, with a fixed incline of 1% and load increment (1km/h) every minute until the maximum speed of the treadmill, at which time the increment of 2% incline begins every minute. The protocol should be started

with 10.9 or 8 km/h according to the time for a 10 km race, with the time below 35', between 35' and 46', and above 46', respectively. Tests should be maximum, being interrupted by limiting symptoms / intense physical fatigue.

The data obtained in this test in conjunction with body composition will be used to stratify the volunteers into four different strata. In addition, the randomization of volunteers in each strata will follow the process: firstly, the researcher [name], will be responsible for creating a computer-generated random list of numbers for the treatment groups of either LcS or placebo, and after each volunteer will be anonymously and sequentially allocated in these groups according to their recruitment ordering number in the program.

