### **Sample collection**

Blood, saliva, and nasal swab will be collected on five different occasions: (1) before the beginning of the ingestion of fermented milk containing LcS or placebo; (2) 24 hours before the triathlon competition; (3) immediately (IM); (4) 72 hours (post-72h); and (5) 14 days after the competition, as shown in Figure 1. In addition, on the same occasions, the occurrence of upper airway symptoms and mood states will also be assessed by using questionnaires.

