### **Statistical analysis**

All data obtained during the development of this study will be added to a unique file, preferentially in an Excel file, which will be available to all researchers not only to consult and check the data quality/accuracy but also to add any results through GOOGLE-DRIVE. It is noteworthy to clarify that, to perform all the statistical analysis proposed here, we will follow the "intention-to-treat" (ITT) analysis, not only because it is recommended as an analysis strategy for randomized studies but also to be possible to maintain the sample size, as well as to use the data obtained from the participants regardless of whether they complete the study since ITT considers all randomized participants in the analysis, whether they drop out or not. In addition, the multiple imputation (MI) method will be applied to handle missing data since

MI fills in missing values by generating plausible numbers derived from distributions of and relationships among observed variables in the data set. Beyond these analyses, in order to check and increase the reliability of the results obtained in the ITT analysis, we also intend to conduct the statistical analysis regarding the per-protocol (PP) analysis, which will be used exclusively the complete data obtained from the volunteers.

After all data will be added to the Excel file and the data quality/accuracy is checked by the researchers, these data will be initially compared with the Gaussian curve, and normality determined for each variable.

If the variable presents a parametric behavior, the mean and standard deviation will be used, and they will be compared by using the ANOVA test for repeated measures with post hoc tests for intragroup (longitudinal) and intergroup (cross-sectional) analysis.

On the other hand, if the data present a non-parametric behavior, they will be represented by median and interquartile ranges, and they will be compared by using Friedman's test with Müller-Dun post hoc test for intragroup (longitudinal) and the Kruskal-Wallis test with Müller Dunn's post hoc test for intergroup (cross-sectional).

Using Pearson (for parametric values) or Spearman tests (for non-parametric values), the correlation between the variables studied will be evaluated.

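### The salivary IgA analysis adjusts for neither the pre-intake value nor the four randomisation strata; at the plan's own correlation of 0.5, baseline adjustment cuts the variance of a single-occasion arm comparison by 25% at almost no cost

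*Combined protocol and SAP*

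**What the plan says.** The primary objective concerns "changes in the concentration of salivary IgA in amateur triathletes" (Objectives, Primary). Of the five saliva samples, the first is taken "before the beginning of the ingestion of fermented milk containing LcS or placebo" (Sample collection), so a true baseline exists.

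Results of the cardiopulmonary test and body composition "will be used to stratify the volunteers into four different strata" (Cardiopulmonary Test), and the same section describes randomisation in each stratum. Trial Design adds that "the randomization will be performed as block randomization with a 1:1 allocation".

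The Statistical analysis section has two branches for continuous outcomes:

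- If normality holds: an "ANOVA test for repeated measures with post hoc tests for intragroup (longitudinal) and intergroup (cross-sectional) analysis".
- If not: Friedman's test with a "post hoc test for intragroup (longitudinal) and the Kruskal-Wallis test" between groups.

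Neither branch names a covariate, an analysis of covariance or a stratum term.

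The sample size (Population and design of the study) uses the G*Power option "repeated measures, within-between interaction option to accommodate the mixed design of the study", with "Correlation among repeated measures: 0.5".

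**The concern.** The trial will hold two pieces of pre-treatment information on randomised athletes, the first IgA value and the stratum, and the plan adjusts for neither.

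In the parametric branch, pre-intake IgA enters only as one of five outcome levels. The group-by-time test can show that the two profiles differ somewhere. The size and timing of the arm difference then come from the cross-sectional post hoc tests, which ignore baseline.

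The non-parametric branch is weaker. Friedman's test works within an arm, so Kruskal-Wallis at each occasion is the only between-arm test, and it uses no baseline. If IgA fails the normality check, the plan has no between-arm test of change, although change is what the primary objective is about.

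Precision is at stake, and so is a pre-specified choice between raw, change-score and adjusted results. Validity is not.

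**Working it through.** **Inputs.** From Population and design of the study: f = 0.15, alpha 0.05, power 0.85, correlation ρ = 0.5, nonsphericity correction 1, two groups, five occasions, N = 62, planned enrolment 70–80. Assumptions made here: a two-sided 5% level for single-occasion contrasts, equal variances, and the same ρ between every pair of occasions (as the sample size calculation has it).

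**1. The plan's own figure.** λ = f²·N·5/(1 − ρ) = 0.0225 × 62 × 5/0.5 = 13.95, with 4 and 240 degrees of freedom, gives power 0.857. N = 60 gives 0.844 and N = 61 gives 0.851, so 62 is the smallest even total. The stated sample size stands.

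**2. One occasion, arm against arm.** Relative to raw values (= 1), the variance factor is 2(1 − ρ) for a change score and 1 − ρ² for baseline as a covariate.

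| ρ | Raw | Change score | Adjusted | Cut vs raw | Cut vs change |
|---|---|---|---|---|---|
| 0.3 | 1 | 1.4 | 0.91 | 9% | 35% |
| 0.5 | 1 | 1.0 | 0.75 | 25% | 25% |
| 0.7 | 1 | 0.6 | 0.51 | 49% | 15% |

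At ρ = 0.5 the standard error falls by 1 − √0.75 = 13%, and a change score gains nothing over raw values.

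Illustrative power for a 0.75 SD difference at ρ = 0.5, before the cost in step 3:

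| Per arm | Raw | Adjusted |
|---|---|---|
| 31 | 0.83 | 0.92 |
| 35 | 0.87 | 0.95 |
| 40 | 0.91 | 0.97 |

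**3. Cost of the extra terms.** With p covariates the variance is multiplied by 1 + p/(N − 2 − p − 1). At N = 62:

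- Baseline alone: 0.75 × (1 + 1/58) = 0.763, a net cut of about 24%. A simulation of 20,000 trials gave 0.774.
- Baseline plus three stratum terms, if the strata are unbalanced between arms and do not predict IgA: 0.75 × (1 + 4/55) = 0.805, a net cut of about 20%. With strata balanced between arms, the simulated ratio stayed at 0.774.

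Net of this cost, the 0.92 at 31 per arm becomes 0.914 with baseline alone and 0.899 in the worst case. The t critical value moves from 2.000 (60 df) to 2.003 (56 df).

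**4. The sized group-by-time test.** Suppose the arms differ by d SD at k of the four later occasions and not elsewhere. Then f² = d²(k − k²/5)/20. Setting f = 0.15 gives d²(k − k²/5) = 0.45, so d = 0.75, 0.61, 0.61 and 0.75 for k = 1 to 4. Given baseline, the later occasions have covariance 0.5·I + 0.25·J (I the identity matrix, J the all-ones matrix), and the adjusted λ = (N/4)·2d²(k − k²/6). The cut is 1 − 13.95/λ at N = 62.

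| k | λ at N = 62 | Variance cut | Power, N = 62 (unadjusted 0.857) | Power, N = 70 (unadjusted 0.902) |
|---|---|---|---|---|
| 1 | 14.53 | 4% | 0.873 | 0.914 |
| 2 | 15.50 | 10% | 0.896 | 0.932 |
| 3 | 17.44 | 20% | 0.930 | 0.958 |
| 4 | 23.25 | 40% | 0.982 | 0.991 |

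These powers omit the slope cost. For k = 1 at N = 62, including it lowers 0.873 to about 0.866.

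**5. The strata.** No correlation between the strata and IgA is given. Trial Design says blocks; the Cardiopulmonary Test section describes a random list with sequential allocation and does not place blocks within strata. Omitting the strata makes the cross-sectional tests conservative only if the strata predict IgA and the arms are balanced within them. Neither can be established, so no stratum gain enters any figure above.

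**The case against.** The strongest reply is that the trial is sized on the group-by-time interaction, which already uses baseline as a level. On that test the gain can be small: with an effect at one later occasion, power rises by less than two points. The 40% cut needs an equal difference at all four later occasions, a pattern the documents do not support. This stands, and it is why the 25% must be read as applying to single-occasion contrasts. Those contrasts are nevertheless what will be read as the effect on IgA at each time, and adjustment helps in every pattern examined.

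Other limits also stand:

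- The correlation of 0.5 is a planning value for all pairs of occasions. The first sample precedes the race by 30 days and the others cluster around and after it. At 0.3 the cut against raw values is only 9%.
- The 0.75 SD illustration is the larger of the differences that match f = 0.15. At 0.61 SD with 31 per arm, power is about 0.66 unadjusted and 0.77 adjusted (net of the slope cost).
- The extra terms are not entirely free, so net figures of 20–24% are the ones to quote.
- The case for the strata rests on matching the analysis to the randomisation, without a measured gain.
- A log scale, a rank-based alternative and extension to other outcomes are design choices; the documents give no IgA distribution and no correlation for those outcomes.

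None of this removes the omission or reverses the direction of the gain.

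**Conclusion.** The concern holds as a loss of precision that should be corrected. For a single-occasion comparison of IgA between arms, baseline adjustment at ρ = 0.5 cuts the variance by 25%, or about 20–24% net at N = 62. For the sized interaction test the cut runs from 4% to 40%, depending on how many later occasions carry the effect. These sizes rest on the plan's assumed correlation, taken as equal across occasions, and on baseline alone. The contribution of the strata is unknown. The sample size is not in question.

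**What to change.** In the Statistical analysis section, specify one model for salivary IgA:

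- Pre-intake log IgA as a covariate, or equivalently arm means constrained to be equal at occasion 1.
- The four randomisation strata as a fixed effect.
- LcS minus placebo with a 95% CI at each of the four later occasions.

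If IgA fails the normality check, keep the adjusted model on the log scale or use a rank-based analysis of covariance, because Kruskal-Wallis by occasion cannot take a covariate. Apply the same adjustment to the other laboratory outcomes and BRUMS where a pre-intake value exists. State also whether blocks are formed within strata. Fix the wording before unblinding.

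The cost is a text change and about four degrees of freedom (one slope, three stratum terms). No new data, visits or participants are needed.

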### **Anamnesis, physical examination, and competition**

At the beginning of the study, all participants will undergo an anamnesis with a cardiovascular and otorhinolaryngological analysis to exclude the presence of cardiovascular diseases and upper airway symptoms resulting from rhinosinusitis, rhinopathies, or any other pre-existing alteration in these systems. In addition, the WURSS (Wisconsin Upper Respiratory Symptom Survey) questionnaire will be used to verify the occurrence of upper airway symptoms not only during this period but also throughout the study period (Annex 1), and the presence of premenstrual syndrome will be self-reported by the female volunteers during the anamnesis.

It is noteworthy to cite that the volunteers will be oriented to maintain their usual daily routine, including sleep, diet, and training/physical activity during the study performance. In this respect, to characterize not only the quality of life (Annex 2) but also the level of physical activity (Annex 3), questionnaires will be applied with open questions about the participants' lifestyle and habits, history and current habits of physical activity, as well as participation in competitions. Beyond these questionnaires, it will be also assessed the occurrence of discomfort or gastrointestinal problems related to the daily intake of fermented milk containing LcS or not by using a questionnaire with open questions about gastrointestinal problems will be used (Annex 4). The volunteers who reported any gastrointestinal discomfort during the ingestion of the fermented milk containing or not LcS will be oriented to immediately interrupt this ingestion and seek medical assistance. In case of the volunteer needs to interrupt the ingestion of fermented milk for five consecutive days, following medical recommendation, this volunteer and its data will be excluded from the study.

It is utmost of importance to point out that all athletes will have medical follow-ups by [name] [name], a specialist in Sports Medicine, throughout the study. Besides, through social media, all volunteers will be able to directly contact not only [name] but also other researchers involved in the study's development in order to communicate any adverse events and other unintended effects of trial interventions.

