In addition, the McNemar Chi-square test (with Yates correction) will be used to determine whether the difference in the number of volunteers who presented or not upper airway symptoms, as well as in the duration of the symptoms, is significantly different in each group (paired analysis). Additionally, Chi-square test will be used to perform the same analysis but between the volunteer groups (unpaired analysis).

A risk of less than to 0.05 ( $p<0.05$ ) will be considered statistically significant for every study.

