#### **SCHEDE OF ACTIVITIES TO BE DEVELOPED**

Parameters	Enrollment	Allocation	Intervention				
			Pre-Triathlon		Post-Triathlon		
Timepoint			-60d to -30d	-30d	-1d	0d	3d
Recruitment and selection of volunteers	X						
Informed consent	X						
Anamnesis, anthropometry, cardiopulmonary test	X						
Randomization		X					
Intervention: LcS/Placebo intake			X	X	X	X	X
Questionnaire - WURSS	X			X		X	X

Questionnaire - IPAQ	X			X			
Questionnaire - gastrointestinal problems	X			X		X	X
Questionnaire – SF36	X			X		X	X
Questionnaire – BRUMS	X			X		X	X
Questionnaire - Subjective Perception of Effort Scale	X				X		
Blood, saliva, nasal swab collection			X	X	X	X	X

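### The five-day interruption rule removes athletes and their data against the intention-to-treat plan, and no by-arm count of gastrointestinal symptoms is planned

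*Combined protocol and SAP*

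**What the plan says.** **Collection.** The section Anamnesis, physical examination, and competition states that "it will be also assessed the occurrence of discomfort or gastrointestinal problems related to the daily intake of fermented milk containing LcS or not". The instrument is Annex IV: 13 symptoms over the past week, each graded in seven steps from none to very intense. The activity schedule carries the row "Questionnaire - gastrointestinal problems" at enrolment and at later visits. No total score, any-symptom variable or scoring rule is given.

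**Stopping and exclusion.** Athletes with discomfort "will be oriented to immediately interrupt this ingestion and seek medical assistance"; the section LcS ingestion repeats the instruction. The next sentence in the Anamnesis section covers a volunteer who has to interrupt intake for five consecutive days on medical advice: "this volunteer and its data will be excluded from the study".

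**Analysis.** The Statistical analysis section adopts intention to treat in order "to use the data obtained from the participants regardless of whether they complete the study", with multiple imputation and a per-protocol analysis alongside. Then "these data will be initially compared with the Gaussian curve, and normality determined for each variable". Normal variables get mean and standard deviation with repeated-measures ANOVA. For the others, "they will be represented by median and interquartile ranges, and they will be compared by using" Friedman's test within groups and Kruskal-Wallis between groups. McNemar and chi-square tests are planned for the "difference in the number of volunteers who presented or not upper airway symptoms" and for symptom duration. No analysis is named for Annex IV.

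**The concern.** Two things affect what a reader will learn about gastrointestinal tolerability, the one intake-related problem for which the protocol has its own questionnaire.

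First, the exclusion rule acts on a post-randomisation event that may be caused by the product. Athletes whose discomfort is bad enough for a doctor to keep them off the drink for five days are the ones the summary most needs. Under this rule they leave it, and with them goes all their other data, which the intention-to-treat text says will be used.

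Second, the protocol asks whether gastrointestinal problems occur but plans counts of affected athletes only for airway symptoms. If single Annex IV items go through the median and interquartile-range rule, uncommon symptoms can give two identical summaries and a p-value. There would be no count, risk difference or interval showing what excess on LcS the data leave possible, and a non-significant result could be taken for good tolerability.

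**Working it through.** **1. The two rules side by side.** Statistical analysis: all randomised participants are analysed, completers or not, with imputation of what is missing. Anamnesis: after five days off the drink on medical advice, the volunteer and the volunteer's data are removed. Both cannot be followed for the same athlete. A per-protocol set already exists, and it is the natural place for the second rule.

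The documents give no interruption rate, so the effect can only be illustrated. Suppose 8/35 on LcS and 1/35 on placebo are affected, and assume that 1, 2 or 3 of the affected LcS athletes are removed:

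- none removed: 8/35 − 1/35 = 22.9% − 2.9% = +20.0 points (95% CI 4.1 to 36.3)
- one: 7/34 − 1/35 = +17.7 points
- two: 6/33 − 1/35 = +15.3 points
- three: 5/32 − 1/35 = +12.8 points (−1.8 to 29.1)

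Intervals here and below are Newcombe intervals built from Wilson limits. For 8/35 the limits are 12.1% and 39.0%; for 1/35 they are 0.5% and 14.5%. Lower limit: 20.0 − √[(22.9 − 12.1)² + (14.5 − 2.9)²] ≈ 4.1. Upper limit: 20.0 + √[(39.0 − 22.9)² + (2.9 − 0.5)²] ≈ 36.3, computed before rounding.

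**2. When the median and both quartiles sit at the floor.** The inputs are 35 to 40 athletes per arm (Population and design of the study) and one item at one visit. With linear interpolation the upper quartile lies at position 1 + 0.75(n − 1).

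- n = 35: position 26.5, so the 27th ordered value must be at the floor. At most 35 − 27 = 8 may be affected (22.9%).
- n = 40: position 30.25, so the 31st must be at the floor. At most 40 − 31 = 9 may be affected (22.5%).

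Under six quartile definitions, every count below 25% gives the floor at n = 35, 36, 39 and 40. At n = 37 and 38, 9 affected (24.3% and 23.7%) lifts the upper quartile under some definitions. The plan does not name its normality test. In simulated items of this kind Shapiro-Wilk always rejected (largest p about 6 × 10⁻⁹), so they would go to the median and interquartile-range branch.

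**3. How often both arms print the floor.** The gastrointestinal rates are assumed. The exact probability is P(X₁ ≤ k) × P(X₂ ≤ k), binomial, with k = 8 for n = 35 and k = 9 for n = 40. For 5% v 20% at n = 35 this is 1.000 × 0.745 = 0.745. The last column is simulated, with affected athletes spread evenly over three grades above the floor.

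| Placebo v LcS (assumed) | Both arms at floor, n = 35 / 40 | Floor and Kruskal-Wallis p ≥ 0.05 |
|---|---|---|
| 5% v 15% | 93.1% / 93.3% | about 67–70% |
| 5% v 20% | 74.5% / 73.2% | about 43–48% |
| 10% v 20% | 74.0% / 72.8% | about 64–66% |
| 5% v 25% | 47.4% / 44.0% | about 20–26% |
| 10% v 30% | 23.3% / 19.5% | about 16–20% |
| 20% v 30% | 17.4% / 14.3% | about 14–17% |
| 30% v 40% | 0.6% / 0.3% | under 1% |

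**4. What counts would show.** The p-values are Kruskal-Wallis on affected yes/no.

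- LcS 6/40 v placebo 2/40: identical floor summaries, p = 0.14. Difference +10.0 points (−4.0 to 24.5).
- LcS 8/35 v placebo 1/35: identical floor summaries, p = 0.013. Difference +20.0 points (4.1 to 36.3). The excess is flagged, but its size is not displayed.
- Equal arms: 3/40 ±13.3, 3/35 ±14.9, 6/40 ±16.2, 5/35 ±17.1, 9/40 ±18.1, 8/35 ±19.4 points.

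**The case against.** The strongest reply is that the plan nowhere says Annex IV will be printed as medians. The general rule speaks of each variable, but read literally it would also cover yes/no items such as premenstrual syndrome or Annex IV's own training question. It is evidently meant for measured quantities. What the plan shows is silence on how Annex IV is scored, and a summed score might avoid the floor. This stands: a reader might infer that the plan commits to an uninformative display, and the documents do not support that. The floor result is conditional on single-item analysis. It remains true that no other stated rule reaches Annex IV, and a sum would still not show how many athletes were affected.

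It also stands that every gastrointestinal rate here is assumed. The Introduction says endurance competition can contribute to gastrointestinal problems, so the floor may not occur on a form covering the race week. A large excess may be caught by its p-value, as at 8/35 v 1/35. A reader might infer that the investigators intend a tolerability claim from a non-significant test; no section plans one.

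Other safeguards exist: fortnightly bottle return, medical follow-up, reports to the ethics committee and a commitment to CONSORT reporting. They monitor intake and safety, but none specifies a by-arm gastrointestinal table.

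Finally, the conflict over exclusion is general and reaches every outcome, and the five-day rule is not worded as limited to gastrointestinal causes. Both are correct. It belongs here because the rule is placed directly after the instruction on gastrointestinal discomfort, and those are the cases it is likely to catch.

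**Conclusion.** The contradiction between the five-day exclusion and the intention-to-treat text holds on any reading, and following the exclusion can take the worst gastrointestinal cases out of the by-arm summary. How many would go cannot be derived from the documents. Nor do they support an inference that the primary salivary IgA comparison is biased in a known direction.

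The display problem holds conditionally. If Annex IV items are analysed singly under the median and interquartile-range rule, an item affecting fewer than about a quarter of each arm generally prints the floor value in both, with the exception at 37 to 38 per arm noted above. Its frequency depends wholly on assumed rates: large for uncommon symptoms and negligible for common ones. What is lost is the size of any LcS excess, not necessarily its detection.

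Severity is minor. Neither the primary nor the secondary objective depends on gastrointestinal symptoms.

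**What to change.** In Anamnesis, physical examination, and competition, replace exclusion of the athlete and data with stopping the product. Keep all recorded data in the intention-to-treat set, and exclude such athletes only from the per-protocol set.

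In Statistical analysis, state that Annex IV symptoms and gastrointestinal-related interruptions of intake will be reported by randomised arm as n/N (%) with risk difference and 95% CI, and that p ≥ 0.05 will not be read as evidence of tolerability. The severity threshold that defines an affected athlete, and how visits are grouped, are for the investigators to choose, provided they are fixed before unblinding.

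The cost is a few lines of text and one or two tables from forms already scheduled. The intervals will be wide, about ±13 to 19 points when the arms are equal, and there is no gain in power.
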